3.2 Inclusion Criteria

Subject is eligible for the study if all of the following apply:

1. Institutional Review Board (IRB)/Independent Ethics Committee (IEC)-approved written informed consent and privacy language as per national regulations (e.g., Health Insurance Portability and Accountability Act Authorization for US sites) must be obtained from the subject or legally authorized representative prior to any study-related procedures (including withdrawal of prohibited medication, if applicable).
2. Subject is considered an adult according to local regulation at the time of signing informed consent form (ICF).
3. Subject has defined AML by the WHO criteria (2017) and fulfills one of the following:
 - Refractory to at least 1 cycle of induction chemotherapy
 - Relapsed after achieving remission with a prior therapy
4. Subject is positive for FLT3 mutation in bone marrow or blood after completion of the subject's last interventional treatment as determined by the local institution.
5. Subject has an ECOG performance status ≤ 2 at screening.
6. Subject must meet the following criteria as indicated on the clinical laboratory tests:
 - Serum AST and ALT ≤ 2.5 x upper limit of normal (ULN)
 - Serum total bilirubin (TBL) ≤ 1.5 x ULN
 - Serum creatinine ≤ 1.5 x ULN or an estimated glomerular filtration rate of > 50 mL/min as calculated by the Modification of Diet in Renal Disease equation.
7. Subject is suitable for oral administration of study drug.
8. A female subject is eligible to participate if she is not pregnant [see [Appendix 12.3 Contraception Requirements](#)] and at least one of the following conditions applies:
 - Not a woman of childbearing potential (WOCBP) as defined in [[Appendix 12.3 Contraception Requirements](#)]

OR

- WOCBP who agrees to follow the contraceptive guidance as defined in [Appendix 12.3 Contraception Requirements] throughout the treatment period and for at least 180 days after the final study drug administration.
9. Female subject must agree not to breastfeed starting at screening and throughout the study period, and for at least 180 days after the final study drug administration.
 10. Female subject must not donate ova starting at screening and throughout the study period, and for at least 180 days after the final study drug administration.
 11. A male subject must not donate sperm starting at screening and throughout the treatment period, and for at least 120 days after the final study drug administration.

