5.4.2 Laboratory Assessments

Refer to [Appendix 12.8 Laboratory Assessment] and laboratory manual for a list of the laboratory tests that will be performed during the conduct of the study. Refer to the Schedule of Assessments [Table 1] for study visit collection dates. Local laboratory tests can be used at screening for eligibility for serum chemistry, hematology, urinalysis and coagulation only. In

the event that the central laboratory results received after enrollment are not within eligibility parameters, the subject will still be considered eligible if local labs met the eligibility criteria and not considered a protocol deviation. Additional laboratory tests should be performed according to institutional standard of care. Local testing of hematology and bone marrow aspirate and/or biopsy at screening and day 1 of each cycle will be reported in the eCRF. Hematology results will need to be assessed prior to dosing.

Clinical significance of out-of-range laboratory findings is to be determined and documented by the investigator/subinvestigator who is a qualified physician.

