12.5 Liver Safety Monitoring and Assessment

Any subject enrolled in a clinical study with active drug therapy and reveals an increase of serum aminotransferases to $> 3 \times \text{ULN}$ or TBL $> 2 \times \text{ULN}$ should undergo detailed testing for liver enzymes (including at least ALT, AST, ALP, and TBL). Testing should be repeated within 72 hours of notification of the test results. For studies for which a central laboratory is used, alerts will be generated by the central laboratory regarding moderate and severe liver abnormality to inform the investigator and study team. Subjects should be asked if they have any symptoms suggestive of hepatobiliary dysfunction.

Definition of Liver Abnormalities

Confirmed abnormalities will be characterized as moderate and severe where ULN:

	ALT or AST		TBL
Moderate	$> 3 \times \text{ULN}$	or	$> 2 \times \text{ULN}$
Severe	$> 3 \times \text{ULN}$	and	$> 2 \times \text{ULN}$

In addition, the subject should be considered to have severe hepatic abnormalities for any of the following:

- ALT or AST $> 8 \times \text{ULN}$.
- ALT or AST $> 5 \times \text{ULN}$ for more than 2 weeks.
- ALT or AST $> 3 \times \text{ULN}$ and International Normalized Ratio (INR) > 1.5 (If INR testing is applicable/evaluated).
- ALT or AST $> 3 \times \text{ULN}$ with the appearance of fatigue, nausea, vomiting, right upper quadrant pain or tenderness, fever, rash and/or eosinophilia ($> 5\%$).

The investigator may determine that abnormal liver function results, other than as described above, may qualify as moderate or severe abnormalities and require additional monitoring and follow-up.

Follow-up Procedures

Confirmed moderate and severe abnormalities in hepatic functions should be thoroughly characterized by obtaining appropriate expert consultations, detailed pertinent history, physical examination and laboratory tests. The site staff is to complete the liver abnormality case report form (LA-CRF). Subjects with confirmed abnormal liver function testing should be followed as described below.

Confirmed moderately abnormal liver function tests (LFTs) should be repeated 2 to 3 times weekly then weekly or less if abnormalities stabilize or the study drug has been discontinued and the subject is asymptomatic.

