12.6 Common Serious Adverse Events

The following is a list of SAEs that the sponsor considers to be associated with the disease state being studied. The list does NOT change your reporting obligations or prevent the need to report an AE meeting the definition of an SAE as detailed in [Section 5.5.2 Definition of Serious Adverse Events]. The purpose of this list is to alert the investigator that some events reported as SAEs may not require expedited reporting to the regulatory authorities based on the classification of “common SAEs”. The investigator is required to follow the requirements detailed in [Section 5.5.5 Reporting of Serious Adverse Events].

For IND safety reporting, single occurrences of the following events may be excluded from expedited reporting to the FDA. If aggregate analysis of these events indicate they occur more frequently with study drug, an expedited IND safety report may be submitted to the FDA.

Serious Adverse Events Caused by AML	Grades Usually Observed with AML
Hematologic AE	
Anemia	0 - 4
Bone marrow hypocellular	0 - 4
CD4 lymphocytes decreased	0 - 4
Disseminated intravascular coagulation	0 - 3
Leukocytosis	0 - 4
Lymphocyte count decreased	0 - 4
Lymphocyte count increased	0 - 4
Neutropenia	0 - 4
Neutrophil count decreased	0 - 4
Platelet count decreased	0 - 4
Purpura	0 - 3
Thrombocytopenia	0 - 4
White blood cell decreased	0 - 4
Infection-related AE	
Bacterial infection (regardless of organ-system involved or specific bacterial cause)	0 - 3
Chills	0 - 3
Cough	0 - 3
Febrile neutropenia (without infection)	0 - 4
Fever	0 - 5
Flu-like symptoms	0 - 3
Fungal infections (regardless of organ-system involved or fungal cause)	0 - 3
Mucositis	0 - 4
Periodontal disease	0 - 3
Pneumonia	0 - 5
Sepsis/septicemia/bacteremia (all causes)	0 - 5
Sinusitis	0 - 4
Sore throat	0 - 3
Psychiatric and Nervous System Related AE	
Anxiety	0 - 2
Cognitive disturbance	0 - 3
Confusion	0 - 5
Depressed level of consciousness	0 - 5
Depression	0 - 3
Table continued on next page	

Serious Adverse Events Caused by AML	Grades Usually Observed with AML
Libido decreased	0 - 2
Meningismus	0 - 5
Seizure	0 - 5
Somnolence	0 - 5
Syncope	3
Other AEs	
Activated partial thromboplastin time prolonged	0 - 2
Alanine aminotransferase increased	0 - 2
Alkaline phosphatase increased	0 - 2
Anorexia	0 - 2
Aspartate aminotransferase increased	0 - 2
Blood bilirubin increased	0 - 2
Bone and/or joint pain	0 - 2
Bruising	0 - 2
Bleeding/hemorrhage	0 - 5
Diarrhea	0 - 2
Dyspnea	0 - 5

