SAP	Statistical Analysis Plan
SBP	Systolic Blood Pressure
SOC	System Organ Class
TEAE	Treatment-Emergent Adverse Event
ULN	Upper Limit of Normal
WHO	World Health Organization
WHO – DD	World Health Organization – Drug Dictionary
WOCBP	Woman of Childbearing Potential

List of Key Terms

Terms	Definition of terms
Baseline	Assessments of subjects as they enter a study before they receive any treatment.
Endpoint	Variable that pertains to the efficacy or safety evaluations of a study.
Enroll	To register or enter a subject into a clinical study. NOTE: Once a subject has received the study drug or placebo, the clinical study protocol applies to the subject.
Intervention	The drug, device, therapy or process under investigation in a clinical study that is believed to have an effect on outcomes of interest in a study. (e.g., health-related quality of life, efficacy, safety and pharmacoeconomics).
Investigational period	Period of time where major interests of protocol objectives are observed, and where the test drug or comparative drug is usually given to a subject, and continues until the last assessment after completing administration of the test drug or comparative drug.
Post investigational period	Period of time after the last assessment of the protocol. Follow-up observations for sustained adverse events and/or survival are done in this period.
Screening	A process of active consideration of potential subjects for enrollment in a study.
Screen failure	Potential subject who did not meet 1 or more criteria required for participation in a study.
Screening period	Period of time before entering the investigational period, usually from the time when a subject signs the consent until just before the test drug or comparative drug is given to a subject.
Study period	Period of time from the first site initiation date to the last site completing the study.
Variable	Any entity that varies; any attribute, phenomenon or event that can have different qualitative or quantitative values.

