7.5.2 Clinical Laboratory Evaluation

The baseline visit is the last measurement taken prior to initial study drug administration.

Quantitative clinical laboratory variables, i.e., hematology, serum chemistry, coagulation and urinalysis will be summarized using mean, standard deviation, minimum, maximum and median at each visit. Additionally, change from baseline will be calculated as the

post-baseline value minus the baseline value and summarized in the same way. Each laboratory result will be classified as low (L), normal (N), or high (H) at each visit according to the laboratory supplied reference ranges.

The number and percentage of subjects below and above reference range will be summarized at each visit.

Frequency tabulations of qualitative clinical laboratory variables (urinalysis) will be presented at each visit.

Clinically significant abnormalities in laboratory values will be presented.

For hematology and chemistry two types of shift tables will be presented:

- Shift tables of changes based on reference range defined category (low, normal, high) from baseline to each visit as well as worst finding during the treatment period, and
- Summary shifts of changes based on reference range defined category from baseline to each visit as well as worst finding during the treatment period (shift from high or normal to low, shift from low or normal to high, categorized increase [shift from low to normal or from normal to high], categorized no change [value stays in the same reference range], categorized decrease [shift from high to normal or from normal to low]).

Laboratory results will also be graded using NCI-CTCAE v5.0, where possible. Parameters that have criteria available for both low and high values, i.e., hypo- and hyper-, will be summarized for both criteria. The same subject can be counted for both values if the subject has different laboratory values meeting each criterion. NCI-CTCAE grade of laboratory evaluations will be summarized by number and percentage of subjects for each visit. Shift tables of NCI-CTCAE grade change from baseline to worst post-baseline grade will also be presented.

Laboratory results based on central assessment will be used for summaries as described above. Laboratory results based on local assessment and bone marrow results will be listed only. The laboratory results may be displayed in figures.

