7.5.2.1 Liver Enzymes and Total Bilirubin

The following potentially clinically significant criteria in liver function tests for Alkaline Phosphatase (ALP), Alanine Transaminase (ALT), total bilirubin, Aspartate Transaminase (AST) and their combination are defined. The subject's highest value during the study will be used.

Parameter	Criteria
ALT	> 3xULN > 5xULN > 8xULN
AST	> 3xULN > 5xULN > 8xULN
ALT or AST	> 3xULN
Total Bilirubin	> 2xULN
ALP	> 1.5xULN
ALT and/or AST AND Total Bilirubin(*)	(ALT and/or AST > 3xULN) and total bilirubin > 2xULN

(*) Combination of values measured within same sample

The number and percentage of subjects with potentially clinically significant values in liver enzymes and total bilirubin will be presented.

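### The liver-enzyme table takes the highest value during the study rather than after the first dose, so pre-dose results, mainly ALP, can be counted

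*SAP*

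**What the plan says.** SAP 7.5.2.1 sets cut-offs for ALT and AST (above 3, 5 and 8xULN, plus either one above 3xULN), total bilirubin (above 2xULN), ALP (above 1.5xULN), and ALT and/or AST above 3xULN together with bilirubin above 2xULN in the same sample. Subjects are classified by one rule: the "highest value during the study will be used". No start point is given.

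The parent section, SAP 7.5.2, uses other windows. Its reference-range shift tables for chemistry run to the "worst finding during the treatment period". For toxicity grades it says: "Shift tables of NCI-CTCAE grade change from baseline to worst post-baseline grade will also be presented". It bases the summaries on central laboratory results; local results are only listed.

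Protocol 3.2 (criterion 6) limits AST and ALT to 2.5xULN and bilirubin to 1.5xULN at entry, without waivers, and says nothing about ALP. Protocol 5.4.2 adds that if "central laboratory results received after enrollment are not within eligibility parameters, the subject will still be considered eligible if local labs met the eligibility criteria". Protocol 12.6 includes "Alkaline phosphatase increased" among events it associates with AML, at grades 0 to 2.

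Protocol 12.5 gives five laboratory or clinical routes to a severe liver abnormality, including ALT or AST above 3xULN with INR above 1.5 (where INR is tested), and ALT or AST above 5xULN for more than two weeks.

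**The concern.** A table of potentially significant liver values is read as a description of what happened on drug. If pre-dose samples can supply the maximum, a subject whose only raised result came before treatment is reported as a finding. The trial has one arm, so no control rate is available to show how much of a row is background disease. Raised ALT and AST are expected reactions to gilteritinib (protocol 1.3.1) and hepatitis is an adverse event of special interest for atezolizumab (protocol 12.7), so these counts will be looked at closely.

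A smaller matter is that the protocol defines severe liver abnormality, but the table cannot say how many subjects met two of its laboratory criteria, those based on INR and on duration.

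**Working it through.** The plan gives no figure to reproduce, so the check sets the texts side by side.

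**1. The window.** The SAP's key terms define the study period as "Period of time from the first site initiation date to the last site completing the study", which has no link to dosing. Chemistry is scheduled at screening and on cycle 1/day 1 (SAP Table 1).

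| SAP table | Window or baseline comparison |
|---|---|
| Reference-range shifts (7.5.2) | worst in treatment period, against baseline |
| CTCAE grade shifts (7.5.2) | worst post-baseline, against baseline |
| Significant vital signs (7.5.3) | threshold and a minimum change from baseline |
| Liver tests (7.5.2.1) | highest during the study, no baseline comparison |

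Of these, only the liver table has neither a post-dose limit nor a baseline comparison.

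**2. Which rows are exposed.** Compare entry limits with the lowest cut-off in each row.

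| Row | Entry limit | Table cut-off | Can a qualifying value trigger it? |
|---|---|---|---|
| ALT, AST | at most 2.5xULN | above 3xULN | No (2.5 < 3) |
| Bilirubin | at most 1.5xULN | above 2xULN | No (1.5 < 2) |
| ALT/AST with bilirubin | both limits | both cut-offs | No |
| ALP | none | above 1.5xULN | Yes |

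For every row except ALP, some pre-dose central result other than the qualifying one must lie above the cut-off. That can happen if central and local results disagree, since eligibility may rest on local results while central ones are summarised. It can also happen if values change between samples before the first dose: a rise by cycle 1/day 1, or a high screening result later repeated (protocol Table 1, footnote h, permits repeats).

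**3. Whose classification changes.** Let B be the subjects above a cut-off before dosing and A those above it at any time after. The present rule counts everyone in A or B; a post-dose rule counts A. The difference is B without A:

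change in count = n × p × r,

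where p is the share above the cut-off before dosing and r is the share of those who are never above it afterwards. The documents give neither p nor r.

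**4. The severe criteria.** The five routes in protocol 12.5 map onto the SAP rows as follows.

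| Protocol 12.5 route | SAP row |
|---|---|
| above 3xULN with bilirubin above 2xULN | own row |
| above 8xULN | own row |
| above 5xULN for more than 2 weeks | within the above-5x row only |
| above 3xULN with INR above 1.5 | within the above-3x rows only |
| above 3xULN with symptoms, rash or eosinophilia | within the above-3x rows only |

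Two of five have their own row. INR is in the coagulation panel (protocol 12.8), so the INR criterion can be derived. Duration needs a rule. From cycle 2, scheduled samples fall on days 1 and 15 of a 28-day cycle, 15 − 1 = 14 days apart, and two consecutive results 14 days apart do not show more than two weeks. Repeats that would settle it may be local, and local results are only listed.

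**The case against.** The case for leaving the table alone has several sound parts.

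- **Baseline is already separated elsewhere.** The chemistry shift tables cover ALP, ALT, AST and bilirubin and show who was abnormal before treatment. This stands, but they use reference-range categories and toxicity grades, so the counts at 1.5, 2, 3, 5 and 8xULN cannot be recovered from them.
- **Programmers may apply a post-dose limit anyway.** The table specifications, which SAP 7.1 cites and which are not part of these documents, may say so. That would settle practice, but the SAP would still state a different rule.
- **The section does not claim to reproduce protocol 12.5.** That is correct. The appendix also works with confirmed abnormalities, retested within 72 hours, and makes the INR criterion conditional on testing. This is why the severe criteria are only a secondary improvement.

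Three stronger readings are tempting, and the documents do not support them.

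- A reader might infer that severe cases are missed. They are not: every INR case is in the above-3x rows and every duration case is in the above-5x row. They are unlabelled.
- A reader might infer that the primary safety result is compromised. The primary safety endpoints are DLTs and adverse events; laboratory results are secondary (protocol 2.3.1 and 2.3.2). Confirmed Hy's law cases reach the DLT endpoint separately.
- A reader might assume that 5% to 25% of subjects have ALP above 1.5xULN before dosing and conclude that 49 × 0.05 = 2.5 to 49 × 0.25 = 12.3 phase 2 subjects are wrongly counted. That range has no source in the documents; protocol 12.6 gives grades, not frequencies. It also sets r to 1. Subjects who stay raised after dosing are counted under either rule, so these figures would be a ceiling under the assumption, not an estimate.

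**Conclusion.** The point holds as a wording defect in one secondary safety table. As written, the maximum can come from a pre-dose sample, which is inconsistent with the windows in SAP 7.5.2. ALP is the row mainly exposed; the ALT, AST, bilirubin and combined rows are exposed only when pre-dose results disagree or change. The effect on any count is limited to subjects above the cut-off before dosing and never after it, and its size cannot be estimated from the documents. It could be zero.

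This rests on reading the sentence literally and on the table specifications not overriding it. The missing INR and duration labels limit what the table can report but do not make its counts wrong. Nothing here touches the CRc test, its alpha or power, or DLT monitoring.

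**What to change.** In SAP 7.5.2.1, replace the sentence with: *the subject's highest value after the first dose of study drug will be used*, through the end of the treatment-emergent window in SAP 6.2.4 (30 days after the last study treatment). No laboratory visit is scheduled after end of treatment, so the upper limit matters only for unscheduled samples. Show each row split by whether the criterion was already met at baseline. The cost is one sentence and one table split, using data already collected; SAP section 1 allows revision before hard lock.

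As a secondary improvement, flag or list subjects with ALT or AST above 3xULN and INR above 1.5, and those above 5xULN for more than two weeks. Use central and local results and state how duration is derived, for example from the first to the last of consecutive qualifying results with none below the cut-off between them. This costs a short derivation rule and a listing. The small downside is that some INR flags will reflect leukemia-related coagulopathy rather than liver injury.

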7.5.3 Vital Signs

The baseline visit is the last measurement taken prior to initial study drug administration.

Vital signs (systolic blood pressure [SBP], diastolic blood pressure [DBP], pulse rate and body temperature) will be summarized using mean, standard deviation, minimum, maximum and median by visit. Additionally, change will be calculated as the post-baseline value minus the baseline value and summarized by visit.

Tables for potentially clinically significant vital signs will be generated using baseline value and highest value.

The following potentially clinically significant criteria are defined:

Vital Sign Variable	Criteria
SBP	≥180 mmHg AND ≥20 mmHg change from baseline
DBP	≥105 mmHg AND ≥15 mmHg change from baseline
Pulse Rate	≥120 bpm AND ≥15 bpm change from baseline

7.5.4 Electrocardiograms (ECGs)

12-lead ECGs will be recorded in triplicate at the scheduled time points. Each ECG tracing will be taken at least 5 minutes apart and transmitted electronically to central reading. The mean of the triplicate ECGs from central read should be used for all final treatment decisions, AE reporting and in the summary for analysis at each visit.

ECG variables including changes from baseline will be summarized using mean, standard deviation, minimum, maximum and median at each visit.

Number and percentage of subjects with normal and abnormal results as assessed by central read for the overall interpretation will be tabulated at each visit. A shift analysis table showing shift in overall ECG interpretation from baseline to each time point will be provided. The worst of the three overall ECG interpretations will be used as the time-specific overall ECG interpretation for a subject.

The QT interval corrected for heart rate by Fridericia’s formula, QTcF, is defined as: $QTc(F) = QT/(RR)^{0.33}$, where RR interval is inversely proportional to heart rate (approximately $RR = 60/\text{heart rate}$).

The QTcF interval will be summarized using frequency tables at each visit for values of clinical importance using the range criteria below.

	QTc Interval Criteria Value (msec)	
	Cumulative Category	Interval Category
Normal	≤ 450	≤ 450
Borderline	> 450	> 450 to ≤ 480
Prolonged	> 480	> 480 to ≤ 500
Clinically significant	> 500	> 500

The QTcF interval will also be summarized by the frequencies of subjects with a change from baseline of clinical importance using the criteria identified below. These summaries will be provided at each visit.

Variable	Change from Baseline	
	Cumulative Category	Interval Category
QTc Interval (msec)	<0	<0
	≥ 0	≥ 0 to ≤ 30
	> 30	> 30 to ≤ 60
	> 60	> 60

Number and percentage of subjects with 12 lead ECG abnormalities at each visit as well as number and percentage of subjects whose 12 lead ECG reading shift from baseline to each visit will be tabulated.

